### **11.3 Potential Confounders**

Age, sex, socio-economic status, Primary diagnosis, Comorbidities.

Renal failure: This affects Troponin T more than Troponin I (TnI) due to molecular size, but may still affect the elimination of TnI.

Anaemia: Sicker patients are likely to be more anaemic due to sepsis, reduced erythropoietin production and functional iron deficiency. It will therefore be difficult to interpret whether TnI rises are due to anaemia, or due to the critical illness underlying the anaemia. A separate subgroup analysis will be carried out looking at anaemia.

Cardiac medications: the presence of beta-blockers and Angiotensin Converting Enzyme Inhibitors (ACE-I) may affect changes in TnI levels. Certain medications e.g. ACEI may be stopped prior to surgery.

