### 3.2 PICO Design

Study design was developed using “Patient Intervention Comparator Outcome” (PICO) method.

**Population:** We will recruit 200 adult patients undergoing emergency surgery for fractured neck of femur, aged over 50 years.

**Intervention:** We will use blood samples taken preoperatively and at 24 and 72 hours by the research team or (where able) leftover serum from routinely collected blood samples to minimise need for venepuncture in these patients. We will perform an ECG on the third postoperative day. Urine will be collected at 2 time points post-operatively (within 24 hours and 4-6 days post-operatively).

**Comparator:** This is an exploratory study in which we are trying to understand the dynamics of serum Troponin I, serum creatinine and urinary MALDI-MS following surgery. We will compare patterns of cardiac and renal injury in anaemic and non-anaemic patients.

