## 9. Subgroups

### 9.1 Anaemia

We will explore cardiac and renal biomarker changes in patients with and without anaemia according to WHO definition and also by current transfusion guidelines. We hope this will inform a study looking at myocardial injury as an endpoint for restrictive versus liberal blood transfusion practice for patients with cardiovascular disease in intensive care. This will enable us to study the range of Troponin values that might occur when the patient becomes eligible for entry to this with a preoperative haemoglobin of 90g/l or less. We will also be able to look at Troponin I levels pre- and post-transfusion. This will not require any further blood samples.

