### 11.2 Data Analysis

We will report main trial outcomes by anaemic and non anaemic groups. Continuous data will be presented as mean (95% CI), or median (IQR) if non-normally distributed. Binary data will be presented as frequency (%). Parametric and non parametric variables will be compared using appropriate statistical tests.

Exploratory analyses will utilize the hsTnI profiles to define the optimum method for defining myocardial injury in a subsequent trial, for example maximum values, AUC analyses, and proportions exceeding threshold values. Comparisons across the two study groups will be used to explore the possible validity of this measure in a subsequent large transfusion trigger trial, specifically whether differences exist between patients with different haemoglobin profiles during the perioperative period. Other analyses will explore the relative associations between markers of kidney injury, anaemia, and other factors using regression analysis. We will report the proportion of eligible patients, Hb concentration distribution between groups and mean red blood cell use across groups with 95% confident intervals (CI).

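### Section 11.3 answers illness confounding of the anaemia–troponin contrast with a subgroup analysis on anaemia itself, and no adjusted troponin analysis is specified

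*Combined protocol and SAP*

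**What the plan says.** Section 11.3 lists potential confounders and comments on three: renal failure, anaemia and cardiac medication. On anaemia it notes that sicker patients tend to be more anaemic and concludes: "It will therefore be difficult to interpret whether TnI rises are due to anaemia, or due to the critical illness underlying the anaemia". The next sentence, which ends the paragraph, is the only action given: "A separate subgroup analysis will be carried out looking at anaemia".

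Anaemia is the grouping variable throughout the plan. Section 3.2 says "We will compare patterns of cardiac and renal injury in anaemic and non-anaemic patients". Section 9.1 looks at biomarker changes "in patients with and without anaemia according to WHO definition and also by current transfusion guidelines". Section 11.2 says "We will report main trial outcomes by anaemic and non anaemic groups".

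For these comparisons section 11.2 leaves the tests unnamed and gives no covariates. Troponin may be summarised in several ways, "for example maximum values, AUC analyses, and proportions exceeding threshold values". The group contrast has a purpose: "Comparisons across the two study groups will be used to explore the possible validity of this measure", with a later transfusion-trigger trial in view. The single sentence on regression relates kidney-injury markers, anaemia and unnamed further factors. Troponin is not named in it, and no confounder from 11.3 is tied to any model.

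The primary objective (4.1.1) is descriptive: how TnI changes over time. The primary outcome in 3.2 is binary, high-sensitivity troponin above the upper reference limit. Section 4.2.1 gives the endpoint simply as postoperative TnI.

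**The concern.** The plan identifies a confounding problem and attaches to it an analysis that cannot address it. A subgroup analysis on the exposure is the exposure comparison again. If illness makes patients both more anaemic and more likely to release troponin, the anaemic and non-anaemic groups will differ in troponin even if haemoglobin has no effect, and regrouping by anaemia leaves that difference in place.

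What is at stake is the choice of endpoint for a later trial. Section 3.1 hopes the study will support troponin in that role, and 11.2 uses the group contrast to explore this. If only the crude contrast is reported, a difference produced by illness could be taken as evidence that troponin responds to haemoglobin, and therefore that a transfusion threshold could move it.

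**Working it through.** The plan has no figure to reproduce: section 11.1 says the 200 patients do not come from a formal power calculation. The check is textual, followed by illustrations of size.

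1. **What the subgroup can do.** Write the crude difference as D = (haemoglobin effect) + b, where b is the part due to illness. Within the anaemic stratum there are no non-anaemic patients, so there is no contrast. Comparing the strata returns D, with b unchanged. Section 9.1 adds a second definition of anaemia, which moves the cut-point; a description at low preoperative haemoglobin to "study the range of Troponin values that might occur"; and TnI before and after transfusion. None of these adjusts the between-group comparison for illness.

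2. **Continuous TnI.** From 11.1: n = 200, half anaemic. Assumed, not in the documents: no haemoglobin effect, illness correlated c with both haemoglobin and log TnI (in the directions that make anaemic patients sicker), and a split at the median haemoglobin.
   - Spurious difference, crude = 2√(2/π)·c². For c = 0.2, 0.3, 0.4 this is 1.596 × 0.04, 0.09, 0.16 = 0.06, 0.14, 0.26 SD.
   - SE for 100 versus 100 = 2/√200 = 0.141 SD; 95% half-width = 1.96 × 0.141 = 0.28 SD.
   - A crude two-sided 5% test rejects in about 7%, 17% and 44% of studies (20,000 simulated studies per setting, agreeing with the noncentral t).

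3. **Effect of adjustment.** With an illness proxy of reliability r (assumed), the remaining difference = 2√(2/π)·c²(1−r) / (1 − (2/π)c²r). At r = 0.5 this is 0.03, 0.07, 0.13 SD, so about half the bias remains. Rejection rates for the two-group test:

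| | c = 0.2 | c = 0.3 | c = 0.4 |
|---|---|---|---|
| crude | 7% | 17% | 44% |
| adjusted, r = 0.3 | 6% | 11% | 26% |
| adjusted, r = 0.5 | 6% | 8% | 16% |
| adjusted, r = 0.7 | 5% | 6% | 9% |

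   Treating haemoglobin as continuous does not avoid the problem: crude rejection is 9%, 25% and 63%, and 6%, 10% and 23% after adjustment at r = 0.5.

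4. **Binary outcome of 3.2.** Assumed: illness in 40–60% of anaemic and 20–30% of non-anaemic patients; injury risk 50–60% with illness and 20–30% without; no anaemia effect. Group risk = p·r₁ + (1−p)·r₀, where p is illness prevalence and r₁, r₀ are the injury risks with and without illness.
   - Mildest case: 0.4×0.5 + 0.6×0.3 = 0.38 versus 0.3×0.5 + 0.7×0.3 = 0.36, a difference of 2 points (RR 1.06).
   - Strongest case: 0.6×0.6 + 0.4×0.2 = 0.44 versus 0.2×0.6 + 0.8×0.2 = 0.28, a difference of 16 points (RR 1.57).
   - With 100 per group, a crude test is positive in about 5% to 66% of studies.

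5. **Room for covariates.** Nine terms: anaemia, age, sex, Charlson index, cardiovascular disease or risk, beta-blocker, ACE inhibitor, preoperative creatinine, preoperative TnI.
   - Linear model: 200/9 = 22 patients per term.
   - Binary outcome: section 1.1 gives troponin release after surgery as up to 40% in some studies. 0.40 × 200 = 80 events, and 80/9 = 8.9 per term. At an assumed 20%, 40/9 = 4.4. The proportion in this cohort is unknown.

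**The case against.** The study is exploratory, no significance rule is attached to this contrast, and 11.3 itself warns that attribution will be difficult. All of that stands and limits the harm. It does not make the stated response work.

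The regression sentence in 11.2 comes just before the confounder section, and its unnamed further factors could include troponin and the listed confounders. That is possible, so a reader should not infer that the plan has no regression or rules out adjustment. The text supports only that an adjusted troponin analysis is not specified.

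Section 9.1 also plans within-patient looks. TnI before and after transfusion, and change from a preoperative value, can hold stable factors such as age and comorbidity fixed. This is a fair point, and the model in step 2, which uses a single TnI value, does not represent those analyses. They do not hold acute illness or time since surgery fixed, and acute illness is the confounder that 11.3 names.

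Leaving the TnI summary open is partly deliberate, because 11.2 means to compare candidate summaries and to look at patients whose haemoglobin courses around surgery differ. This stands: the remedy should not force one summary or one definition of anaemia.

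Finally, adjustment reaches the named confounder only weakly, because section 8 lists no preoperative measure of acute illness severity. At reliability 0.3 and c = 0.4 the adjusted test still rejects in 26% of studies. This also stands, and it is why residual confounding must be stated.

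**Conclusion.** The point holds as a gap in the analysis text. The one action attached to illness confounding repeats the exposure comparison, and the troponin contrast as written has no covariates. It should be corrected, but it does not defeat the study.

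Two stronger readings are tempting and are not supported. One is that the primary objective is compromised; it is descriptive and does not depend on this contrast. The other is that the contrast will be materially biased; the documents give no correlation between illness, haemoglobin and troponin, so the size is unknown. Under the assumed correlations the spurious difference runs from 0.06 SD, where the false-positive rate is close to nominal, to 0.26 SD, which is about the width of the sampling error. The bias therefore matters mainly at the upper end of those assumptions. Adjustment would reduce it, by about half at an assumed proxy reliability of 0.5, and would not remove it.

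**What to change.** In 11.3, stop presenting the anaemia subgroup as the response to confounding and keep the 9.1 groupings as description.

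In 11.2, state that each troponin comparison by anaemia or haemoglobin group will be reported both crude and adjusted for baseline variables that section 8 already collects:
- age and sex (from the demographic data), Charlson index, cardiovascular risk factors or disease as recorded, cardiac medication and preoperative creatinine;
- with and without preoperative TnI, because that sample is taken after the fracture;
- not adjusted for transfusion given after the haemoglobin measurement.

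Apply this to the 3.2 outcome (troponin above the upper reference limit) and to the continuous summaries, for example log peak TnI. Use a shorter covariate set for the binary outcome, since events may number about 80 or fewer. Keep the planned comparisons of TnI summaries and of perioperative haemoglobin profiles.

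Explain the two 11.3 confounders left out: primary diagnosis is the same for everyone under 6.2, and socio-economic status is not named in section 8 (add it if it is held with the demographic data). State that residual confounding by acute illness remains, because no preoperative measure of its severity is listed.

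The cost is a few sentences and modest extra analysis, with no new samples. The downsides are that bias is only partly removed, and that adjusted results, especially if they change with preoperative TnI, need careful wording. The difference in sampling times between sections 3.2 and 5 and section 8 is a separate point to reconcile.

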### **12. Trial management and oversight arrangements**

This study will be run in coordination with the Edinburgh Clinical Trials Unit (ECTU).

As this is a purely observational study the likelihood of adverse events is low however we will use ECTU protocols for audit and monitoring.

## Appendix A Flow Chart Study Recruitment

**Appendix B Postoperative Morbidity Survey (POMS)**

Pulmonary	De novo requirement for supplemental oxygen or other respiratory support (e.g., mechanical ventilation or CPAP)
Infectious	Currently on antibiotics or temperature >38 °C in the last 24 h
Renal	Presence of oliguria (<500 mL/d), increased serum creatinine (>30% from preoperatively), or urinary catheter in place for a nonsurgical reason
Gastrointestinal	Unable to tolerate an enteral diet (either by mouth or via a feeding tube) for any reason, including nausea, vomiting, and abdominal distension
Cardiovascular	Diagnostic tests or therapy within the last 24 h for any of the following: de novo myocardial infarction or ischemia, hypotension (requiring pharmacological therapy or fluid therapy >200 mL/h), atrial or ventricular arrhythmias, or cardiogenic pulmonary oedema
Neurological	Presence of a de novo focal deficit, coma, or confusion/delirium
Wound complication	Wound dehiscence requiring surgical exploration or drainage of pus from the operation wound with or without isolation of organisms
Haematological	Requirement for any of the following within the last 24 h: packed erythrocytes, platelets, fresh-frozen plasma, or cryoprecipitate
Pain	Surgical wound pain significant enough to require parenteral

## Appendix C Complication Definitions

### Major Adverse Cardiac Events

**Myocardial infarction:** Any cardiac ischaemic event fulfilling 3rd Universal Definitions for Myocardial Infarction

**Myocardial Injury after Non-cardiac Surgery:** Troponin elevation within 30 days of surgery which does not satisfy universal definitions for myocardial infarction.

**Arrhythmia:** ECG evidence of rhythm disturbance resulting in a fall in mean arterial pressure of greater than 20% or requiring treatment (anti-arrhythmic agents, vasoactive agents, intra venous fluid, etc.).

**Cardiac or respiratory arrest:** As per UK Resuscitation Council Guidelines.

**Cardiogenic pulmonary oedema:** Appropriate clinical history and examination with consistent chest radiograph.

**Pulmonary embolism:** Computed tomography (CT) pulmonary angiogram, clinical or echocardiographic evidence with appropriate clinical history.

### Infectious Complications

**Infection, source uncertain:** Two more of the following associated with strong clinical suspicion of infection (sufficient to require intra-venous antibiotic therapy, etc.):

- (i) Core temperature  $<36^{\circ}\text{C}$  or  $>38^{\circ}\text{C}$
- (ii) white cell count  $>12 \times 10^9 \text{ L}^{-1}$  or  $<4 \times 10^9 \text{ L}^{-1}$
- (iii) (iii) respiratory rate  $>20$  breaths per minute or  $\text{PaCO}_2 < 4.5 \text{ kPa}$
- (iv) (iv) pulse rate  $>90 \text{ bpm}$

**Urinary tract infection:** A symptomatic urinary tract infection must meet at least one of the following criteria:

(i) Patient has at least one of the following signs or symptoms with no other recognized cause: fever ( $>38^{\circ}\text{C}$ ), urgency, frequency, dysuria, or supra-pubic tenderness *and* patient has

a positive urine culture, that is,  $>10^5$  microorganisms per cm^3 of urine with no more than two species of microorganisms.

(ii) Patient has at least two of the following signs or symptoms with no other recognized cause: fever ( $>38C$ ), urgency, frequency, dysuria, or supra-pubic tenderness and at least one of the following:

- a. Positive dipstick for leucocyte esterase and/or nitrate;
- b. Pyuria (urine specimen with  $>10$  WBC mm^-3);
- c. Organisms seen on Gram stain of unspun urine;
- d. At least two urine cultures with repeated isolation of the same uro-pathogen with  $>10^2$  colonies/ mL in non-voided specimens;
- e.  $>10^5$  colonies/mL of a single uro-pathogen in a patient being treated with an effective antimicrobial agent for a urinary tract infection;
- f. physician diagnosis of a urinary tract infection;
- g. physician institutes appropriate therapy for a urinary tract infection.

**Other infections of the urinary tract (kidney, ureter, bladder, urethra, etc.):** Other

infections of the urinary tract must meet at least one of the following criteria:

(i) Patient has organisms isolated from culture of fluid (other than urine) or tissue from affected site.

(ii) Patient has an abscess or other evidence of infection seen on direct examination, during a surgical operation, or during a histopathology examination.

(iii) Patient has at least two of the following signs or symptoms with no other recognized cause: fever ( $>38C$ ), localized pain, or localized tenderness at the involved site and at least one of the following:

- a. Purulent drainage from affected site;
- b. Organisms cultured from blood that are compatible with suspected site of infection;
- c. Radiographic evidence of infection, for example, abnormal ultrasound, computed tomography or magnetic resonance imaging;
- d. Physician diagnosis of infection of the kidney, ureter, bladder, urethra, or tissues surrounding the retroperitoneal or perinephric space;
- e. Physician institutes appropriate therapy for an infection of the kidney, ureter, bladder, urethra, or tissues surrounding the retroperitoneal or perinephric space.

**Surgical site infection (SSI) (superficial incisional):** A superficial SSI must meet the following criteria:

(i) Infection occurs within 30 days after the operative procedure and involves only skin and subcutaneous tissue of the incision and patient has at least one of the following:

- a. Purulent drainage from the superficial incision;
- b. Organisms isolated from an aseptically obtained culture of fluid or tissue from the superficial incision;
- c. At least one of the following signs or symptoms of infection: pain or tenderness, localized swelling, redness, or heat, and superficial incision is deliberately opened by surgeon, unless incision is culture-negative;
- d. Diagnosis of superficial incisional SSI by the surgeon or attending physician.

**Surgical Site Infection (deep incisional):**

A deep incisional SSI must meet the following criteria:

i) Infection occurs within 30 days after the operative procedure if no implant is left in place or within 1 year if implant is in place and the infection appears to be related to the operative procedure and involves deep soft tissues (e.g., fascial and muscle layers) of the incision and patient has at least one of the following:

- a. Purulent drainage from the deep incision but not from the organ/space component of the surgical site;
- b. A deep incision spontaneously dehisces or is deliberately opened by a surgeon when the patient has at least one of the following signs or symptoms: fever ( $>38C$ ) or localized pain or tenderness, unless incision is culture-negative;
- c. An abscess or other evidence of infection involving the deep incision is found on direct examination, during reoperation, or by histopathology or radiologic examination;
- d. Diagnosis of a deep incisional SSI by a surgeon or attending physician.

An infection that involves both superficial and deep incision sites should be classified as a deep incisional SSI.

**Surgical Site Infection (organ/space)**

An organ/space SSI involves any part of the body, excluding the skin incision, fascia, or muscle layers, which is opened or manipulated during the operative procedure. Specific sites are assigned to organ/space SSI to further identify the location of the infection. An example is appendectomy with subsequent sub-diaphragmatic abscess, which would be reported as

an organ/space SSI at the intra-abdominal specific site. An organ/space SSI must meet the following criteria:

- i) Infection occurs within 30 days after the operative procedure if no implant is left in place or within 1 year if implant is in place and the infection appears to be related to the operative procedure and infection involves any part of the body, excluding the skin incision, fascia, or muscle layers, that is opened or manipulated during the operative procedure and patient has at least one of the following:
  - a. Purulent drainage from a drain that is placed through a stab wound into the organ/space;
  - b. Organisms isolated from an aseptically obtained culture of fluid or tissue in the organ/space;
  - c. An abscess or other evidence of infection involving the organ/space that is found on direct examination, during reoperation, or by histopathology or radiologic examination;
  - d. Diagnosis of an organ/space SSI by a surgeon or attending physician.

**Laboratory Confirmed Bloodstream Infection:** Laboratory confirmed bloodstream infection must meet at least one of the following criteria:

- i) Patient has a recognized pathogen cultured from one or more blood cultures and the organism cultured from blood is not related to an infection at another site.
- ii) Patient has at least one of the following signs or symptoms: fever ( $>38C$ ), chills, or hypotension and at least one of the following:
  - a. Common skin contaminant is cultured from two or more blood cultures drawn on separate occasions.
  - b. Common skin contaminant is cultured from at least one blood culture from a patient with an intravascular line, and the physician institutes appropriate antimicrobial therapy.
  - c. Positive antigen test on blood.

Signs and symptoms and positive laboratory results are not to be related to an infection at another site.

**Nosocomial pneumonia:** Nosocomial pneumonia will be characterized as early or late onset i.e. before or after first 4 days of hospitalisation. Where repeated episodes of nosocomial pneumonia are suspected, a combination of new signs and symptoms and radiographic evidence or other diagnostic testing will be required to distinguish a new episode from a previous one. This category includes ventilator-associated pneumonia (i.e. pneumonia in persons who had a device to assist or control respiration continuously through a

tracheostomy or endotracheal tube), however care will be taken to distinguish between tracheal colonization, upper respiratory tract infections and early onset pneumonia.

Nosocomial pneumonia must meet the following criteria:

i) Two or more serial chest radiographs with at least one of the following:

- a. New or progressive and persistent infiltrate;
- b. Consolidation;
- c. Cavitation.

And at least one of the following:

- a. Fever ( $>38C$ ) with no other recognized cause;
- b. Leukopenia ( $WCC < 4 \times 10^9 L^{-1}$ ) or leucocytosis ( $WCC > 12 \times 10^9 L^{-1}$ )
- c. For adults  $>70$  years old, altered mental status with no other recognised cause.

And at least two of the following:

- a. New onset of purulent sputum or change in character of sputum, or increased respiratory secretions, or increased suctioning requirements
- b. New onset or worsening cough, or dyspnoea, or tachypnoea;
- c. Rales or bronchial breath sounds;
- d. Worsening gas exchange

